### 2.1.3 Inclusion of Women and Minorities

Men and women of all races and ethnic groups are eligible for this trial.

### 2.1.4 Recruitment Strategies

The study will be posted on the CCR website and on clinicaltrials.gov.

## 2.2 SCREENING EVALUATION

### 2.2.1 Screening activities performed prior to obtaining informed consent

Minimal risk activities that may be performed before the subject has signed a consent include the following:

- Email, written, in person or telephone or video communications with prospective subjects
- Review of existing medical records to include H&P, laboratory studies, etc.
- Review of existing MRI, x-ray, or CT images
- Review of existing photographs or videos
- Review of existing pathology specimens/reports from a specimen obtained for diagnostic purposes.

### 2.2.2 Screening activities performed after a consent for screening has been signed

The following activities will be performed only after the subject has signed the consent for study #01-C-0129 on which screening activities will be performed. Assessments performed at outside facilities or on another NIH protocol within the timeframes below may also be used to determine eligibility once a patient has signed the consent.

Studies should be done within 28 days prior to enrollment unless otherwise noted below.

- Complete history (including prior hormone use) and physical examination (including height, weight, vital signs, EKG, and performance status).
- CT scan of chest, abdomen and pelvis (or MRI liver (if clinically indicated) (may be done at an outside institution)
- Laboratory Evaluation
  - Hematological profile: CBC with differential and platelet count
  - PT, INR, aPTT, fibrinogen
  - Biochemical profile: electrolytes, BUN, creatinine, AST, ALT, total and direct bilirubin, calcium, phosphorus, albumin, magnesium

- Uric acid and amylase
- Gamma glutamyltransferase (if clinically indicated).
- Urinalysis
- Serum or urine pregnancy test for female participants of childbearing age (in the absence of prior hysterectomy). Test to be performed within 72 hours prior to enrollment.
- Histologic confirmation (at any time point prior to enrollment). A block or unstained slides of primary or metastatic tumor tissue will be required from each participant to confirm diagnosis with analysis being performed by the Laboratory of Pathology, NIH. As stated in the inclusion criteria above, histopathological confirmation of carcinoma may be sufficient. Fibrolamellar variant is also allowed.

### **2.3 PARTICIPANT REGISTRATION AND STATUS UPDATE PROCEDURES**

Registration and status updates (e.g., when a participant is taken off protocol therapy and when a participant is taken off-study) will take place per CCR SOP ADCR-2, CCR Participant Registration & Status Updates found here.

#### **2.3.1 Treatment Assignment Procedures (For registration purposes only):**

##### **Cohorts**

Number	Name	Description
1	A1	First 10 Subjects with Advanced HCC, BCLC Stage C
2	A2	Subjects with Advanced HCC, BCLC Stage B/C
3	B	Subjects with Intra/extra-hepatic cholangiocarcinoma

## Arms

Number	Name	Description
1	A1	Durvalumab + Tremelimumab
2	A2	Durvalumab + Tremelimumab + TACE
3	A3	Durvalumab + Tremelimumab + RFA
4	A4	Durvalumab + Tremelimumab + Cryo

Subjects in cohort A1 will be directly assigned to arm A1.

Subjects in cohort A2 will be directly assigned to arms A2, A3 or A4 per consultation with the interventional radiologists. The reason for this is that there are technical considerations (size and location of lesion, main portal vein occlusion etc.) which would make one procedure preferable over the other. 10 evaluable subjects will be assigned to each intervention.

The first 10 subjects in cohort B will be directly assigned to arm A1.

The remaining subjects in Cohort B will be directly assigned to arms A3 or A4 per consultation with the interventional radiologists. The reason for this is that there are technical considerations (size and location of lesion, main portal vein occlusion etc.) which would make one procedure preferable over the other. 10 evaluable subjects will be assigned to each intervention.

## 2.4 BASELINE EVALUATION

Baseline evaluations do not need to be repeated if performed during Screening within designated time-frame.

Within 28 days prior to first dose, unless otherwise specified:

- CT scan of chest, abdomen and pelvis (or MRI of liver if clinically indicated)
- Electrocardiogram
- Laboratory evaluation
  - Hepatitis B and/or C viral load and serology
  - HLA-A, HLA-B, HLA-C and HLA-A\*02 phenotype (may be done at any time prior to treatment)
  - AMA & Liver/kidney microsomal antibody
  - ANA
  - Rectal swab (optional)
  - Serum or urine pregnancy test for female participants of childbearing age (in the absence of prior hysterectomy, within 72 hours prior to first dose)
- Research tumor biopsy.

### 3 STUDY IMPLEMENTATION

#### 3.1 STUDY DESIGN

The proposed study is a pilot study combining tremelimumab and durvalumab treatment in patients with advanced HCC (Cohorts A1 and A2) either alone (Arm A1) or with cryoablation, TACE or RFA (Arms A2, A3, A4) and patients with advanced BTC (Cohort B) either alone (Arm A1) or with cryoablation or RFA (Arms A3, A4).

The decision on which interventional radiologic procedure to administer (i.e. RFA vs. TACE vs. cryoablation) will be made in consultation with the interventional radiologists. The reason for this is that there are technical considerations (size and location of lesion, main portal vein occlusion etc.) which would make one procedure preferable over the other.

- Transarterial chemoembolization is percutaneous procedure performed under general anesthesia or conscious sedation. (See 3.5.1 for details)
- Patients undergoing trans-arterial chemoembolization, RFA or cryoablation are pre-medicated with analgesics, antibiotics and anti-emetics per clinical standards. For details regarding each procedure please see 3.5.

Cohort	Population	Immune stimulating procedure	Dose level	Planned N
A1	Advanced HCC, BCLC Stage C	No ablative procedure	Tremelimumab 75mg flat dose q28 days for 4 doses Durvalumab 1500mg flat dose q28 days until EOS###	10 total
A2	Advanced HCC, BCLC Stage B/C	Cryoablation/ RFA/TACE*	Tremelimumab 75mg flat dose q28 days for 4 doses Durvalumab 1500mg flat dose q28 days until EOS**	30 total 10 trem+ dur + TACE 10 trem + dur + RFA 10 trem + dur + cryo
B	Intra/extra-hepatic cholangiocarcinoma	N= 1st 10 pts: No ablative procedure  RFA/ cryoablation	Tremelimumab 75mg flat dose q28 days for 4 doses Durvalumab 1500mg flat dose q28 days until EOS**	30 total 10 trem+ dur alone 10 trem + dur + RFA 10 trem + dur + cryo

\* For BCLC stage B patients TACE may be repeated as per standard of care

\*\* EOS = end of study treatment as defined in section 3.8.1.

### **3.2 SCHEDULE**

#### **3.2.1 Cohort A1**

- All 10 patients with BCLC Stage C will receive combined immune checkpoint inhibition only i.e. no interventional radiologic procedure.
- Patients will receive 1500 mg durvalumab via IV infusion q4w for up to 4 doses/cycles and 75 mg tremelimumab via IV infusion q4w for up to 4 doses/cycles, and then continue 1500 mg durvalumab q4w. Tremelimumab will be administered first. Durvalumab infusion will start approximately 1 hour after the end of tremelimumab infusion. The duration will be approximately 1 hour for each infusion. A 1-hour observation period is required after the first infusion of durvalumab and tremelimumab. If no clinically significant infusion reactions are observed during or after the first cycle, subsequent infusion observation periods can be at the Investigator's discretion (suggested 30 minutes after each durvalumab and tremelimumab infusion).

#### **3.2.2 Cohort A2**

The schema for Cohort A2 is shown below. For Cohort A2 (BCLC Stage B/C patients) TACE, RFA or cryoablation will be performed once only, on Day 36 (+/- 96hrs).

- Both BCLC stage B and C are eligible for cohort A2.
- Patients will receive 1500 mg durvalumab via IV infusion q4w for up to 4 doses/cycles and 75 mg tremelimumab via IV infusion q4w for up to 4 doses/cycles, and then continue 1500 mg durvalumab q4w. Tremelimumab will be administered first. Durvalumab infusion will start approximately 1 hour after the end of tremelimumab infusion. The duration will be approximately 1 hour for each infusion. A 1-hour observation period is required after the first infusion of durvalumab and tremelimumab. If no clinically significant infusion reactions are observed during or after the first cycle, subsequent infusion observation periods can be at the Investigator's discretion (suggested 30 minutes after each durvalumab and tremelimumab infusion).

[figure not shown]

Figure 3: Schema cohort A2

### 3.2.3 Cohort B

The schema for Cohort B is shown below. For Cohort B (BTC patients, status post prior chemotherapy with intrahepatic disease) RFA or cryoablation will be performed once only, on Day 36 (+/- 96hrs). The first N=10 patients will not undergo an ablative procedure i.e. they will receive drug only.

- The first N=10 patients will receive combined immune checkpoint inhibition only i.e. no interventional radiologic procedure.
- Patients will receive 1500 mg durvalumab via IV infusion q4w for up to 4 doses/cycles and 75 mg tremelimumab via IV infusion q4w for up to 4 doses/cycles, and then continue 1500 mg durvalumab. Tremelimumab will be administered first. Durvalumab infusion will start approximately 1 hour after the end of tremelimumab infusion. The duration will be approximately 1 hour for each infusion. A 1-hour observation period is required after the first infusion of durvalumab and tremelimumab. If no clinically significant infusion reactions are observed during or after the first cycle, subsequent infusion observation periods can be at the Investigator's discretion (suggested 30 minutes after each durvalumab and tremelimumab infusion).

[figure not shown]

Figure 4: Schema cohort B

### 3.3 DRUG ADMINISTRATION

#### 3.3.1 Tremelimumab Drug Administration

The first day of dosing is considered Day 1. Each dose of investigational product should be administered using the following guidelines:

- 1) Investigational product must be administered at room temperature (25°C) by controlled infusion at a rate of 250 mL/hour via an infusion pump into a peripheral vein. Prior to the start of the infusion, ensure that the bag contents are at room temperature to avoid an infusion reaction due to the administration of the solution at low temperatures.
- 2) Investigational product must **not** be administered via IV push or bolus but as a slow IV infusion. The entire contents of each IV bag will be infused using an infusion pump.
- 3) The infusion lines should be attached only at time of use. Lines used for infusion during dose administration will need to be equipped with 0.22 or 0.2 µm in-line filters.
- 4) If there are no requirements to slow, interrupt, or permanently stop the infusion, the anticipated infusion time to deliver each dose (250 mL) is anticipated to be approximately 60 minutes.

The duration of the investigational product administration will be recorded.

#### 3.3.2 Durvalumab Drug Administration

Each dose of durvalumab should be administered using the following guidelines:

- 1) Durvalumab will be administered as an IV infusion over approximately 60 minutes.

- 2) When an IV bag is used for the infusion, the IV line will be flushed with a volume of normal saline equal to the priming volume of the infusion set used after the contents of the IV bag are fully administered (unless prohibited by institutional practice).
- 3) Since the compatibility of durvalumab with other IV medications and solutions, other than normal saline (0.9% [w/v] Sodium Chloride for Injection), is not known, the durvalumab solution should not be infused through an IV line in which other solutions or medications are being administered.
- 4) The duration of the investigational product administration will be recorded.

### 3.3.3 Monitoring of Dose Administration

Vital signs will be collected before investigational product infusion and at the completion of the infusion.

In the event of a  $\leq$  grade 2 infusion-related reaction, the infusion rate of study drug may be decreased by 50% or interrupted until resolution of the event and re-initiated at 50% of the initial rate until completion of the infusion. For patients with a  $\leq$ Grade 2 infusion related reaction, subsequent infusions may be administered at 50% of the initial rate. Acetaminophen and/or an antihistamine (e.g., diphenhydramine) or equivalent medications per institutional standard may be administered at the discretion of the investigator. If the infusion related reaction is  $\geq$ Grade 3 or higher in severity, study drug will be discontinued. The standard infusion time is one hour, however, if there are interruptions during infusion, the total allowed time from infusion start to completion of infusion should not exceed 8 hours at room temperature (otherwise requires new infusion preparation).

As with any antibody, allergic reactions to dose administration are possible. Therefore, appropriate drugs and medical equipment to treat acute anaphylactic reactions must be immediately available, and study personnel must be trained to recognize and treat anaphylaxis, as per local institutional guidelines.

## 3.4 DOSING DELAYS

The following broad guidelines for dose delivery schedule delays and alternations apply to both planned dosages of tremelimumab and durvalumab and are dependent on the clinical and laboratory assessment on the day of dosing. Tremelimumab and durvalumab can be delivered within 7 days of planned interval to accommodate scheduling issues/logistics.

### 3.4.1 Immune-mediated AEs (imAEs)

Based on the mechanism of action of durvalumab and tremelimumab leading to T-cell activation and proliferation, there is the possibility of observing immune-mediated AEs (imAEs) during the conduct of this study. Potential imAEs may be similar to those seen with the use of ipilimumab, BMS-936558 (anti-PD-1 mAb), and BMS-936559 (anti-PD-L1 mAb) and may include immune-mediated enterocolitis, dermatitis, hepatitis (hepatotoxicity), and endocrinopathies[4, 34, 35]. These AEs are inflammatory in nature and can affect any organ.

Subjects should be monitored for signs and symptoms of imAEs. In the absence of an alternate etiology (e.g., infection or PD), an immune-mediated etiology should be considered for signs or symptoms of enterocolitis, dermatitis, hepatitis, and endocrinopathy. Dosing modification and management guidelines for imAEs specified in [Appendix F](#).

### 3.4.2 Adverse Events of Special Interest

An adverse event of special interest (AESI) is one of scientific and medical interest specific to understanding of the investigational product and may require close monitoring and rapid communication by the investigator to the sponsor. An AESI may be serious or non-serious. The rapid reporting of AESIs allows ongoing surveillance of these events in order to characterize and understand them in association with the use of this investigational product.

AESIs for durvalumab and tremelimumab include but are not limited to events with a potential inflammatory or immune-mediated mechanism and which may require more frequent monitoring and/or interventions such as steroids, immunosuppressants and/or hormone replacement therapy. These AESIs are being closely monitored in clinical studies with durvalumab monotherapy and combination therapy. An immune-mediated adverse event (imAE) is defined as an adverse event that is associated with drug exposure and is consistent with an immune-mediated mechanism of action and where there is no clear alternate etiology. Serologic, immunologic, and histologic (biopsy) data, as appropriate, should be used to support an imAE diagnosis. Appropriate efforts should be made to rule out neoplastic, infectious, metabolic, toxin, or other etiologic causes of the imAE.

AESIs observed with durvalumab and tremelimumab include:

- Diarrhea / Colitis and intestinal perforation
- Pneumonitis / ILD
- Hepatitis / transaminase increases
- Endocrinopathies (i.e. events of hypophysitis/hypopituitarism, adrenal insufficiency, hyper- and hypothyroidism and type I diabetes mellitus)
- Rash / Dermatitis
- Nephritis / Blood creatinine increases
- Pancreatitis / serum lipase and amylase increases
- Myocarditis
- Myositis / Polymyositis
- Neuropathy / neuromuscular toxicity (i.e. Guillain-Barre, and myasthenia gravis)
- Other inflammatory responses that are rare / less frequent with a potential immune-mediated etiology include, but are not limited to, pericarditis, sarcoidosis, uveitis and other events involving the eye, skin, hematological and rheumatological events, vasculitis, non-infectious meningitis and non-infectious encephalitis.

For current list of adverse drug reactions (ADR)s for durvalumab, please, see [Appendix G](#)

Further information on these risks (e.g. presenting symptoms) can be found in the current version of the durvalumab and tremelimumab Investigator Brochure. For durvalumab and tremelimumab, AESIs will comprise the following:

#### 3.4.2.1 Pneumonitis

AEs of pneumonitis are also of interest for AstraZeneca, as pneumonitis has been observed with use of anti-PD-1 mAbs (but not with anti-PD-L1 mAbs). Initial work-up should include a high-resolution CT scan, ruling out infection, and pulse oximetry. Pulmonary consultation is highly recommended. Guidelines for the management of patients with immune-mediated AEs (imAEs) including pneumonitis are provided in [Appendix F](#).

#### 3.4.2.2 Infusion reactions

AEs of infusion reactions (also termed infusion-related reactions) are of special interest to AstraZeneca and are defined, for the purpose of this protocol, as all AEs occurring from the start of IP infusion up to 48 hours after the infusion start time. For all infusion reactions, SAEs should be reported to AstraZeneca Patient safety as described in Section [7.4](#).

#### 3.4.2.3 Hypersensitivity reactions

Hypersensitivity reactions as well as infusion-related reactions have been reported with anti PD-L1 and anti-PD-1 therapy[[34](#)]. As with the administration of any foreign protein and/or other biologic agents, reactions following the infusion of mAbs can be caused by various mechanisms, including acute anaphylactic (IgE-mediated) and anaphylactoid reactions against the mAbs and serum sickness. Acute allergic reactions may occur, may be severe, and may result in death. Acute allergic reactions may include hypotension, dyspnea, cyanosis, respiratory failure, urticaria, pruritus, angioedema, hypotonia, arthralgia, bronchospasm, wheeze, cough, dizziness, fatigue, headache, hypertension, myalgia, vomiting, and unresponsiveness. Guidelines for the management of patients with hypersensitivity (including anaphylactic reaction) and infusion-related reactions are provided in [Appendix F](#).

#### 3.4.2.4 Hepatic function abnormalities (hepatotoxicity)

Hepatic function abnormality is defined as any increase in ALT or AST to greater than  $3 \times$  ULN and concurrent increase in total bilirubin to be greater than  $2 \times$  ULN. Concurrent findings are those that derive from a single blood draw or from separate blood draws taken within 8 days of each other. Follow-up investigations and inquiries will be initiated promptly by the investigational site to determine whether the findings are reproducible and/or whether there is objective evidence that clearly supports causation by a disease (e.g., cholelithiasis and bile duct obstruction with distended gallbladder) or an agent other than the IP. Guidelines for management of patients with hepatic function abnormality are provided in [Appendix F](#).

Due to the fact that in HCC patients elevated transaminase and/or bilirubin levels are common and fluctuant as a result of underlying liver disease (e.g. viral hepatitis), the toxicity criteria outlined in [Appendix F](#) will be interpreted with the following caveats:

- 1) For patients with HCC with normal liver transaminases and/or bilirubin at baseline, the criteria apply as outlined in [Appendix F](#). (i.e. if a grade 2 event occurs treatment will be held until resolution to grade 1)
- 2) For patients with HCC who have elevated liver transaminases and/or bilirubin at baseline (grade 1 or 2 i.e. still allowing for study entry), subsequent occurrences of grade 2 elevations will not result in holding of therapy.
- 3) Grade 3 events will be treated as per [Appendix F](#) irrespective of baseline levels.

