#### **3.8.1 Criteria for Removal from Protocol Therapy**

An individual subject will not receive any further investigational product if any of the following occur in the subject in question:

- Pregnancy or intent to become pregnant
- Any AE that meets criteria for discontinuation as defined in section 3.4.
- Patient decides to withdraw from the study
- Adverse event related to durvalumab or tremelimumab, with the exception of toxicities that do not meet the criteria for discontinuation as defined in section 3.4 if applicable
- Grade  $\geq 3$  infusion reaction
- Initiation of alternative anticancer therapy including another investigational agent
- Confirmation of PD and investigator determination that the subject is no longer benefiting from treatment with durvalumab + tremelimumab
- Investigator discretion

Subjects who are permanently discontinued from further receipt of investigational product, regardless of the reason (withdrawal of consent, due to an AE, other), will be identified as having permanently discontinued treatment.

Subjects who are permanently discontinued from receiving investigational product will be followed for safety per Section 7, including the collection of any protocol-specified blood specimens, unless consent is withdrawn or the subject is lost to follow-up or enrolled in another clinical study. Subjects who decline to return to the site for evaluations will be offered follow-up

by phone every 3 months as an alternative. All subjects will be followed for survival by phone call or e-mail every 6 months.

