### 4.4 CONCOMITANT TREATMENT(S)

The Principal Investigator must be informed as soon as possible about any medication taken from the time of screening until the end of the clinical phase of the study (final study visit). Any concomitant medication(s), including herbal preparations, taken during the study will be recorded in the CRF.

Restricted, prohibited, and permitted concomitant medications are described in the following tables. Refer to Section 3.4 for guidance on management of IP-related toxicities.

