## 8.5.2 Other events requiring reporting

### 8.5.2.1 Overdose

Any overdose of a study subject with durvalumab + tremelimumab, with or without associated AEs/SAEs, is required to be reported within 24 hours of knowledge of the event to the sponsor and AstraZeneca/MedImmune Patient Safety or designee using the designated Safety e-mailbox (see Section 8.5.1 for contact information). If the overdose results in an AE, the AE must also be recorded as an AE (see Section 16.5). Overdose does not automatically make an AE serious, but if the consequences of the overdose are serious, for example death or hospitalization, the event is serious and must be recorded and reported as an SAE (see Section 16.5). There is currently no specific treatment in the event of an overdose of durvalumab or tremelimumab.

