### 8.5.2.2 Hepatic function abnormality

Hepatic function abnormality (as defined in Section 3.4.2.) in a study subject, with or without associated clinical manifestations, is required to be reported as “hepatic function abnormal” ***within 24 hours of knowledge of the event*** to the sponsor and AstraZeneca/MedImmune Patient Safety using the designated Safety e-mailbox (see Section 7.4 for contact information), unless a definitive underlying diagnosis for the abnormality (e.g., cholelithiasis or bile duct obstruction) that is unrelated to investigational product has been confirmed.

- If the definitive underlying diagnosis for the abnormality has been established and is unrelated to investigational product, the decision to continue dosing of the study subject will be based on the clinical judgment of the investigator.
- If no definitive underlying diagnosis for the abnormality is established, dosing of the study subject must be interrupted immediately. Follow-up investigations and inquiries must be initiated by the investigational site without delay.

Each reported event of hepatic function abnormality will be followed by the investigator and evaluated by the sponsor and AstraZeneca/MedImmune.

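### Caveat 2 of section 3.4.2.4 makes no exception for the combined transaminase and bilirubin rise for which section 8.5.2.2 requires interruption, and the protocol does not say which rule prevails

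*Combined protocol and SAP*

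**What the plan says.** Section 3.4.2.4 defines hepatic function abnormality as ALT or AST above 3 x ULN with total bilirubin above 2 x ULN, from one blood draw or from draws within 8 days of each other. It asks for prompt follow-up and refers onward for management: "Guidelines for management of patients with hepatic function abnormality are provided in" Appendix F. Because raised and variable liver tests are common in HCC, it adds that the Appendix F criteria "will be interpreted with the following caveats":

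- Caveat 1, for HCC patients with normal transaminases and/or bilirubin at baseline: Appendix F applies as written, so that "if a grade 2 event occurs treatment will be held until resolution to grade 1".
- Caveat 2, for HCC patients with raised transaminases and/or bilirubin at baseline (grade 1 or 2): "subsequent occurrences of grade 2 elevations will not result in holding of therapy".
- Caveat 3: grade 3 events follow Appendix F whatever the baseline.

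Section 8.5.2.2 takes the same definition and applies it to any study subject, with no HCC or baseline exemption. It requires a report within 24 hours unless a confirmed unrelated diagnosis explains the values. On dosing it states: "If no definitive underlying diagnosis for the abnormality is established, dosing of the study subject must be interrupted immediately". Investigator judgment on continuing applies only once an unrelated diagnosis is established.

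**The concern.** Caveat 2 carries no carve-out for the combined pattern, although that pattern is defined a few lines above it. An HCC patient with raised baseline tests can therefore have an event that caveat 2 says needs no hold and that 8.5.2.2 says must stop dosing. Nothing states which rule governs, and 3.4.2.4 does not point to 8.5.2.2.

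What is at stake is the work-up interval. An investigator who applied caveat 2 as written could give the next dose while a possible drug-induced liver injury was still unexplained. The patients concerned already have abnormal liver tests. Section 12.5.1.2 lists hepatitis under tremelimumab as capable of causing liver failure and death.

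A second problem lies inside the caveats. Both populations are worded with *and/or*, so a patient with one test normal and the other raised at baseline belongs to both.

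**Working it through.** This is a check of consistency between rules; the plan gives no figure to reproduce.

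**Inputs**

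- Abnormality definition (3.4.2.4): ALT/AST > 3 x ULN and bilirubin > 2 x ULN.
- Grade 2: the HCC rows of Appendix F carry no grades, so grade 2 is read from the general hepatitis row: ALT/AST > 3 to 5 and bilirubin > 1.5 to 3. These are multiples of ULN if baseline is normal and of baseline if it is abnormal.
- Appendix F HCC rows, baseline raised. First level: ALT/AST up to 5 x ULN, no change. Second level: > 2.0 x baseline and up to 12.5 x ULN, hold until 5 x ULN or below. Third level: > 12.5 to 20 x ULN, hold, with permanent stop rules including Hy's law.
- Step-up in the HCC rows: use the next level if bilirubin reaches 1.5 x ULN (normal baseline) or 2 x baseline (raised baseline).

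**Step 1. Can one event be grade 2 and also meet the definition?**

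- ULN band: ALT > 3 to 5 lies wholly above 3. Bilirubin > 1.5 to 3 exceeds 2 over the range > 2 to 3. The rules overlap.
- Baseline band, taking baseline ALT 1.5 and bilirubin 1.2 x ULN: ALT runs from 3 x 1.5 = 4.5 to 5 x 1.5 = 7.5 x ULN. Bilirubin runs from 1.5 x 1.2 = 1.8 to 3 x 1.2 = 3.6 x ULN, and exceeds 2 over > 2 to 3.6. They overlap again.

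**Step 2. Two constructed patients, both now at ALT 4.5 and bilirubin 2.5 x ULN**

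| | Patient A | Patient B |
|---|---|---|
| Baseline ALT, bilirubin (x ULN) | 1.3, 1.2 | 1.3, 0.9 |
| ALT / baseline | 4.5/1.3 = 3.46 | 4.5/1.3 = 3.46 |
| Bilirubin / baseline | 2.5/1.2 = 2.08 | normal baseline; use 2.5 x ULN |
| Grade 2 on both tests | yes, on both the ULN and baseline scales | yes |
| Definition met (4.5 > 3, 2.5 > 2) | yes | yes |
| Caveat 1 | does not apply | hold |
| Caveat 2 | do not hold | do not hold |
| 8.5.2.2, no diagnosis yet | interrupt | interrupt |

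**Step 3. Appendix F without the caveat.** For Patient A, ALT at 3.46 x baseline exceeds 2.0 x baseline and is below 12.5 x ULN. That is the second HCC level, a hold whatever the bilirubin. Bilirubin at 2.08 x baseline passes the 2 x baseline trigger, so dosing is managed at the third level. ALT of 4.5 x ULN also fits the first level; starting there, the step-up leads to the second level, which is still a hold. Patient B reaches the same result, because 2.5 x ULN passes the 1.5 x ULN trigger. The release value of 5 x ULN is already met at 4.5, so in practice the hold lasts only if steroids are started, since resumption then waits for a completed taper.

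**Step 4. Hy's law.** Caveat 2 speaks only of holding, so it does not cancel the permanent stop. That stop requires the absence of any alternative cause, so it does not cover the time spent looking for one.

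**Step 5. How many patients?** The documents give no rates. The following are assumptions on the 40 planned HCC patients, with 2 to 10% of each group showing the pattern.

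- Both tests raised in 10 to 40%: 40 x 0.10 x 0.02 = 0.08 to 40 x 0.40 x 0.10 = 1.6.
- One test raised in 15 to 40%: 40 x 0.15 x 0.02 = 0.12 to 40 x 0.40 x 0.10 = 1.6.

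These ranges are not reduced for the further conditions that both values stay within grade 2, that no diagnosis is found, and that a dose falls due during work-up.

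**The case against.** The strongest reply is that the protocol, read as a whole, already gives the stricter answer. Caveat 2 is introduced as a way of interpreting Appendix F and nothing else. Section 8.5.2.2 is a separate mandatory rule covering every subject, placed directly beneath the 24-hour reporting duty, so an investigator who reports the event will meet it. This reading is available, and someone who reads both sections would interrupt. It does not remove the point: the precedence has to be inferred, and the section that sets the hold rules does not cite the one that overrides them.

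A reader might infer that section 3.4 directs dosing to continue through suspected liver injury. The documents do not support that. Caveat 2 removes an automatic hold; it does not compel a dose. The opening of section 3.4 describes its rules as broad and dependent on assessment on the dosing day, section 3.4.2.10 asks for a risk-benefit judgment before continuing in immune-mediated events, and Study Calendar footnote f requires safety bloods to be reviewed before each infusion.

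A reader might also infer that the protocol steers investigators away from 8.5.2.2. The evidence is weak. Section 3.8.1 ("Any AE that meets criteria for discontinuation as defined in section 3.4") lists grounds for permanent removal, not temporary holds. Section 4.4 ("Refer to Section 3.4 for guidance on management of IP-related toxicities") is a cross-reference in the concomitant-treatment text. What does stand is that the interruption rule sits under "Other events requiring reporting".

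Finally, whether a caveat written in grades can switch off HCC rows that have none is itself unclear. That is fair, and it is another reason to settle the wording. The relaxed hold for isolated fluctuations is a reasoned choice and is not challenged here.

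**Conclusion.** The concern holds in this limited form. For HCC patients with raised baseline tests, caveat 2 and 8.5.2.2 give opposite dosing instructions for a grade 2 event that meets the abnormality definition. They can be reconciled, but the protocol does not say how. When only one test is raised at baseline, caveats 1 and 2 also contradict each other.

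The overlap in Step 1 follows from the printed thresholds. It assumes only that grade 2 means the general Appendix F row, and it appears on either scale. The number of patients is an assumption throughout and probably small: 0.08 to 1.6 with both tests raised and a further 0.12 to 1.6 with one raised, both likely too high for the reasons given. The case for changing the text rests on the consequence of a wrong dose, not on frequency.

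BTC patients, grade 3 events, and HCC patients with both tests normal at baseline are not affected. Sample size and analysis are untouched.

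**What to change.** Add one clause to caveat 2: it does not apply when the hepatic function abnormality definition in 3.4.2.4 is newly met on study. Dosing is then interrupted per 8.5.2.2 until a definitive unrelated cause is established, and Appendix F discontinuation for Hy's law continues to apply. Isolated rises stay under caveat 2.

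For the combined pattern this also settles the conflict between caveats 1 and 2, since both then stop dosing. Two gaps remain. The *and/or* overlap persists for isolated rises. Patients who already meet the definition at entry are not covered: ALT/AST up to 5 x ULN is eligible, and with cirrhosis bilirubin is limited only through Child-Pugh (2.1.1.8).

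The cost is a few held doses in HCC patients with fluctuating liver tests, which 8.5.2.2 already requires. No tests or patients are added. In cycles 1 to 4 chemistry is weekly, so detection on day 8, 15 or 22 leaves 29 - 8 = 21, 29 - 15 = 14 or 29 - 22 = 7 days before the next planned dose; detection on day 1 leaves none. After cycle 4 chemistry is scheduled only on day 1, so detection there means a same-day hold. A dose up to 7 days late stays within the section 3.4 window; a longer work-up delays the cycle.
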